1.5.3 Warnings and Precautions associated with the use of PIO (Package insert)

Congestive Heart Failure; PIO, like other TZD, can cause dose-related fluid retention when used alone or in combination with other antidiabetic medications and is most common when PIO is used in combination with insulin. Fluid retention may lead to or exacerbate congestive heart failure. Patients should be observed for signs and symptoms of congestive heart failure.

Hypoglycemia; Patients receiving PIO in combination with insulin or other antidiabetic medications (particularly insulin secretagogues such as sulfonylureas) may be at risk for hypoglycemia. A reduction in the dose of the concomitant antidiabetic medication may be necessary to reduce the risk of hypoglycemia.

Hepatic Effects; There have been post-marketing reports of fatal and non-fatal hepatic failure in patients taking PIO, although the reports contain insufficient information necessary to establish the probable cause. There has been no evidence of drug-induced hepatotoxicity in the PIO controlled clinical trial database to date. Patients with type 2 diabetes may have fatty liver disease or cardiac disease with episodic congestive heart failure, both of which may cause liver test abnormalities, and they may also have other forms of liver disease, many of which can be treated or managed. Patient who develop abnormal liver tests (ALT greater than 3 times the upper limit of the reference range); PIO treatment should be interrupted.

Urinary Bladder Tumors; Tumors were observed in the urinary bladder of male rats in the two-year carcinogenicity study. In two 3-year trials in which PIO was compared to placebo or glyburide, there were 16/3656 (0.44%) reports of bladder cancer in patients taking PIO compared to 5/3679 (0.14%) in patients not taking PIO. After excluding patients in whom exposure to study drug was less than one year at the time of diagnosis of bladder cancer, there were six (0.16%) cases on PIO and two (0.05%) cases on placebo. A five-year interim report of an ongoing 10-year observational cohort study found a no significant increase in the risk for bladder cancer in subjects ever exposed to PIO, compared to subjects never exposed to PIO (HR 1.2 [95% CI 0.9 –1.5]). Compared to never exposure, a duration of PIO therapy longer than 12 months was associated with an increase in risk (HR 1.4 [95% CI 0.9 –2.1]), which reached statistical significance after more than 24 months of PIO use (HR 1.4 [95% CI 1.03 –2.0]). Interim results from this study suggested that taking PIO longer than 12 months increased the relative risk of developing bladder cancer in any given year by 40% which equates to an absolute increase of three cases in 10,000 (from approximately seven in 10,000 [without PIO] to approximately 10 in 10,000 [with PIO]). There are insufficient data to determine whether PIO is a tumor promoter for urinary bladder tumors. Consequently, PIO should not be used in patients with active bladder cancer and the benefits of glycemic control versus unknown risks for cancer recurrence with PIO should be considered in patients with a prior history of bladder cancer.

Edema; In controlled clinical trials, edema was reported more frequently in patients treated with PIO than in placebo-treated patients and is dose-related. In post marketing experience, reports of new onset or worsening edema have been received. PIO should be used with caution in patients with edema. Because TZD, including PIO, can cause fluid retention, which can exacerbate or lead to congestive heart failure, PIO should be used with caution in patients at risk for congestive heart failure. Patients treated with PIO should be monitored for signs and symptoms of congestive heart failure.

Fractures; In PROactive (the Prospective Pioglitazone Clinical Trial in Macrovascular Events), 5238 patients with type 2 diabetes and a history of macrovascular disease were randomized to PIO (N=2605), and were force-titrated up to 45 mg daily or placebo (N=2633) in addition to standard of care. During a mean follow-up of 34.5 months, the incidence of bone fracture in females was 5.1% (44/870) for PIO versus 2.5% (23/905) for placebo. This difference was noted after the first year of treatment and persisted during the course of the study. The majority of fractures observed in female patients were non-vertebral

fractures including lower limb and distal upper limb fractures. No increase in the incidence of fracture was observed in men treated with PIO (1.7%) versus placebo (2.1%).

Macular Edema; Macular edema has been reported in post marketing experience in diabetic patients who were taking PIO or another TZD. Some patients presented with blurred vision or decreased visual acuity, but others were diagnosed on routine ophthalmologic examination. Most patients had peripheral edema at the time macular edema was diagnosed. Some patients had improvement in their macular edema after discontinuation of the TZD.

Ovulation; Therapy with PIO, like other TZD, may result in ovulation in some premenopausal anovulatory women. As a result, these patients may be at an increased risk for pregnancy while taking PIO. This effect has not been investigated in clinical trials, so the frequency of this occurrence is not known. Adequate contraception in all premenopausal women treated with PIO is recommended.

Macrovascular Outcomes; There have been no clinical studies establishing conclusive evidence of macrovascular risk reduction with PIO or any other antidiabetic drug.

1.5.4 Contraindications for the use of PIO (Package insert):

PIO is contraindicated in the following settings:

- Hypersensitivity to PIO or any component of the formulation;
- New York Heart Association (NYHA) Class III/IV heart failure
- pregnancy
- serious hepatic impairment (Canadian labeling)
- Active bladder cancer; history of bladder cancer; uninvestigated macroscopic hematuria (Canadian labeling)

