Figure 7. Study schema

Subjects may enter the study before or after restarting the TKI that was previously discontinued. Disease status can therefore be $>$ MMR but still in CCyR and CHR or \leq MMR. Subject will start PIO in addition to TKI, at 30mg/d for 2 cycles (56 days) and, in the absence of grade 2 or higher toxicities, PIO doses will be increased to 45mg/d. If grade 2 or higher toxicities occur on PIO 45 mg/d, PIO dose will be held until toxicities are \leq grade 1, and PIO doses will be decreased to 30 mg/d (**Dose modification was described section 7.1**). Subjects will receive PIO in addition to TKI for 6 months from the first documented \leq MR^{4,5}. During the combination of PIO and TKI, subjects will be monitored by blood qRT-PCR for *BCR-ABL1* obtained monthly.

Subjects entering the study in $>$ MMR but still in CCyR and CHR who do not achieve MMR within 4 months of the combination of PIO and TKI will be taken off study. Subjects entering the study in \leq MMR or who achieve MMR within 4 months of combination of PIO and TKI, will receive PIO for 6 months from the first documented \leq MR^{4,5}. Subjects who lose MMR at any time on the combination of PIO and TKI will be taken off treatment. Subjects who fail to achieve \leq MR^{4,5} after 6 months of the combination will also be taken off treatment. Fluctuations of PCR from MR^{4,5} at \leq MMR levels are expected and are acceptable during the combination of PIO and TKI.

Subjects who maintain \leq MR^{4,5} for 6 months with less or equal than 2 *BCR/ABL1* transcript fluctuation $<$ MMR will be eligible for a second TKI discontinuation trial. Subjects who discontinue TKI will be monitored by blood qRT-PCR for *BCR-ABL1* obtained monthly for the first 3 months, quarterly for 1 year, and then bi-annually for 1 year. After 2 years of follow-up off TKI, or if MMR is lost off TKI, subjects will have completed their participation on the trial and will enter the Long-Term Follow-up which includes once a year update on disease status (qRT-PCRs) for 5 years.

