3. Participation in another clinical trial with any investigative drug within 30 days prior to study enrolment
4. Chronic graft-versus-host disease requiring systemic immunosuppression post-allogeneic hematopoietic stem cell transplantation
5. Cardiovascular disease: history of congestive heart failure, myocardial infarction within the 6 months of study entry, symptomatic cardiac arrhythmia requiring treatment
6. History of bladder cancer
7. Gross (visible) hematuria
8. Known history of osteoporosis
9. Known history of macular edema
10. Known history of ABL1-domain mutation that predicts resistance to the discontinued TKI
11. Significant medical or psychiatric disorder that would interfere with consent, study participation, or follow-up
12. Known allergy to PIO
13. Pregnant or breastfeeding
14. Use of TZD within 28 days prior to enrollment

15. Significant gastrointestinal condition that could potentially impair the absorption or disposition of the drug
16. Uncontrolled peripheral edema (2+ or more) of any etiology.
17. Active cancer that requires therapy in the form of chemotherapy or radiation

5. Study Procedures

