- Review and document all inclusion and exclusion criteria to ensure that subjects meet all inclusion criteria and none of the exclusion criteria.
- Record AEs as part of standard of care.
- Dispense PIO at 30 mg/d and instruct subjects how to take study drug, daily every 24 hours and how to fill the diary card.

5.2.3 **Visits 3 (Days 14 \pm 2): Early Follow-up**

- Measure and record height in cm and weight in kg. Record vital signs. Measure body temperature, systolic/diastolic BP and pulse rate. Perform and record physical examination.

- Record medications including start/stop dates, indication, dose and frequency for any changes since previous visit.
- Collect blood samples for CBC with differential count and serum chemistries.
- Assess study drug compliance by pill count, review of the diary card and MMAS-8.
- Assess and record AEs and SAEs

5.2.4 Visits 4+ (Day 28 ±2, then q28+/-2 days during combination of PIO and TKI)

- On day 28, measure and record height in cm and weight in kg. Record vital signs. Measure body temperature, systolic / diastolic BP and pulse rate. Perform and record physical examination. Unless new symptoms occur, these will be performed every other month as part of standard of care.
- On day 28, record medications including start/stop dates, indication, dose and frequency for any changes since previous visit. Unless new symptoms occur, these will be performed every other month as part of standard of care.
- On day 28, collect blood samples for CBC with differential count and serum chemistries. Unless new symptoms occur, these will be performed every other month as part of standard of care.
- On day 56, in the absence of grade 2 or higher toxicities, PIO doses will be increased to 45 mg/d
- Dispense drug supply for self-dosing, remind subjects of dosing instructions, and obtain all unused study drug
- Assess study drug compliance by pill count, review of the diary card and MMAS-8.
- Collect blood samples for qRT-PCR of *BCR/ABL1* every month.
- Assess and record AEs and SAEs continuously

5.2.5 Post-discontinuation of PIO and TKI Visits (Monthly for 3 months ± 2 days and quarterly ±7 days for 1 year and biannually thereafter)

- Collect blood samples for qRT-PCR of *BCR/ABL1* as part of standard of care
- Assess and record AEs and SAEs continuously

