7.1 Dose Selection, Treatment Administration, Compliance, and Dose Modifications

The starting dose of PIO will be 30 mg and will be taken orally once daily. After 56 days of PIO 30 mg/d, the dose will be increased to 45 mg/d in the absence of grade >1 related AE. The dose of PIO was selected based on previously published pilot report [47].

Subjects will take the prescribed tablets at approximately the same time each day, regardless of meals. Subjects will be provided a diary card where the date and time of administration will be recorded (**Appendix 1**). Subjects who forget to take their dose can make up the missed dose as long as this is done within the 12 hours of the due time. Any missing dose should be recorded. Drug compliance will be measured using the Morisky Medication Adherence Scales-8 (MMAS8) at every visit while on PIO and TKI (**Appendix 2**). Dose modification will be done as follows:

Table 4. Dose Modification

Toxicity		Immediate action	Later action
Hematologic toxicity	≥ Grade 3 Neutropenia or Thrombocytopenia	1. Hold PIO and TKI until ≤ Grade 1	1. First episode: resume TKI and PIO without dose modifications 2. Second episode: resume at 1 lower dose level (previous dose -15 mg) 3. Third episode: permanent discontinuation of PIO, resume TKI alone
	≤ Grade 3 anemia	1. Continue PIO 2. RBC transfusion if indicated	1. First episode: resume TKI and PIO without dose modifications 2. Second episode: resume PIO at 1 lower dose level (previous dose -15 mg) 3. Third episode: permanent discontinuation of PIO, resume TKI alone
	Grade 4 anemia	1. Hold PIO and TKI 2. RBC transfusion if indicated	1. First episode: resume PIO at 1 lower dose level (previous dose -15 mg) 2. Second episode: permanent discontinuation of PIO, resume TKI alone
Non-hematologic toxicity	Grade 2	1. Hold PIO until ≤ Grade 1	1. First episode: resume TKI and PIO without dose modifications 2. Second episode: resume at 1 lower dose level (previous dose -15 mg)
	≥ Grade 3*	1. Hold PIO and TKI until ≤ Grade 1	1. First episode: resume PIO at 1 lower dose level (previous dose -15 mg) 2. Second episode: permanent discontinuation of PIO, resume TKI alone

*In case of cardiac toxicity, subject will be taken off the study

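### Gross hematuria and bladder cancer bar entry but appear in no on-study dosing rule, so pioglitazone may continue (if graded 1) or resume without investigation

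*Combined protocol and SAP*

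**What the plan says.** Background. Section 1.5.4 gives this entry in its list of PIO contraindications: "Active bladder cancer; history of bladder cancer; uninvestigated macroscopic hematuria (Canadian labeling"). It sets no severity grade. Section 1.5.3 says separately that "PIO should not be used in patients with active bladder cancer"; for a prior history it asks only that benefit and risk be weighed. The bladder paragraph in 1.5.3 does not mention hematuria.

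Entry. Section 4.2 excludes "History of bladder cancer" and "Gross (visible) hematuria".

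On study:
- Escalation, 5.2.4: "On day 56, in the absence of grade 2 or higher toxicities, PIO doses will be increased to 45 mg/d". Section 3.1 has the same grade condition. Section 7.1 adds relatedness: "the dose will be increased to 45 mg/d in the absence of grade >1 related AE".
- Dose modification, Table 4: the non-hematologic rows start at grade 2. At grade 2 PIO is held, and at grade 3 or higher PIO and the TKI are held, in both cases until grade 1 or less. PIO then resumes after a first episode, at the same dose (grade 2) or one level lower (grade 3 or higher). A second episode of grade 3 or higher ends PIO. The only organ-specific note is for cardiac toxicity.
- After grade 2 or higher toxicity on 45 mg, 3.1 also holds PIO to grade 1 or less, and then "PIO doses will be decreased to 30 mg/d".
- Withdrawal, 5.5: names pregnancy and grade 3 or higher cardiac toxicity, with several general criteria.
- Section 8.2.1 makes any new cancer a serious adverse event.

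**The concern.** The protocol treats uninvestigated visible hematuria and bladder cancer as reasons not to give PIO, and acts on that at screening. The same events arising during treatment fall under rules that look at toxicity grade and, in places, relatedness. The contraindication turns on something else: whether the bleeding has been investigated. Bleeding can settle to grade 1 or less before anyone has looked for its cause, and at that point the dosing rules allow PIO again.

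Pregnancy, another 1.5.4 contraindication, is carried into 5.5 and 8.3.1 as an explicit stop, so event-specific stops are already part of this protocol's design. What is at stake is the protection of an individual subject, not the efficacy result.

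**Working it through.** There is no stated figure to reproduce. The check has two parts.

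**1. Follow the rules literally, by grade.** The CTCAE grades for hematuria are not reproduced in the documents, so every case is conditional on the grade assigned.

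| Event | Immediate action | Day-56 increase to 45 mg | Return to PIO | Investigation required before PIO? |
|---|---|---|---|---|
| Visible hematuria, grade 1 | None (no Table 4 row) | Proceeds (3.1, 5.2.4, 7.1) | Not interrupted | No |
| Grade 2, first episode | PIO held (Table 4) | Blocked by 3.1 and 5.2.4; by 7.1 only if related | At grade 1 or less | No |
| Grade 3, first episode | PIO and TKI held | As for grade 2 | At grade 1 or less, one dose level lower | No |
| Second episode, grade 3 or higher | PIO and TKI held | Not applicable | PIO ended | Not applicable |
| New bladder cancer | Serious adverse event report (8.2.1) | Not addressed by name | Not addressed by name | No PIO stop attached |

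**2. How often might bladder cancer arise?** Inputs are from 1.5.3, with 26 subjects from 9.4. The longest planned course under 3.1 is up to 6 months to reach MR4.5 plus 6 months after it, so 12 months.

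(a) The two 3-year trials. There were 16 cases in 3656 PIO patients. After removal of patients whose "exposure to study drug was less than one year at the time of diagnosis of bladder cancer, there were six (0.16%) cases on PIO", so 16 − 6 = 10 cases had under one year of exposure. For patients not on PIO there were 5 in 3679 with 2 remaining, so 5 − 2 = 3 (taking the 2 placebo cases as the remainder of the 5).
- PIO: 10/3656 = 0.274%; 26 × 0.00274 = 0.071 expected cases; chance of at least one = 1 − (1 − 0.00274)^26 = 6.9%. The exact 95% interval for the rate, 0.131% to 0.502%, gives 0.034 to 0.131 expected cases.
- Not on PIO: 3/3679 = 0.082%; 26 × 0.00082 = 0.021.
- If all 26 stopped at 4 months, with cases spread evenly over the year: 0.071 × 4/12 = 0.024.

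(b) The cohort study, about 7 per 10,000 a year without PIO and 10 per 10,000 with PIO (the latter for use beyond 12 months).
- Without PIO: 26 × 0.0007 = 0.018; chance of at least one = 1 − (1 − 0.0007)^26 = 1.8%.
- With PIO: 26 × 0.0010 = 0.026; chance of at least one = 1 − (1 − 0.0010)^26 = 2.6%.

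Across these sources the expected number over one year is about 0.02 to 0.07. The 6.9% is the highest of the point estimates: it assumes all 26 subjects take PIO for the full 12 months and uses only the early cases. The documents give no rate for gross hematuria, so none is calculated.

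**The case against.** The strongest reply is that the existing rules already do most of the work.

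- At grade 2 or higher the hold is compulsory, so only a grade 1 label lets PIO continue or rise. This stands. The remaining gap at the higher grades is resumption without a required work-up.
- Section 5.5 stops PIO for intolerable toxicity, for grade 4 toxicity possibly associated with PIO, for a related non-hematologic interruption of more than 28 days, and for any reason the investigator judges sufficient. Sections 5.2.6 and 8.2.3 provide for work-up. Section 9.6 puts the trial on hold after grade 3-4 toxicity in 2 subjects, 11.4 sets weekly safety review and committee oversight, and 5.6 and 12.4 allow termination. This also stands as partial cover, but none of it ties the return of PIO to a completed investigation.
- The 1.5.4 entry is tagged as Canadian labeling, while the trial is single-center with reporting to the FDA. That weakens any claim that the label obliges a hold. It does not remove the inconsistency, because 4.2 adopts gross hematuria as an exclusion and 1.5.3 bars PIO in active bladder cancer without that tag.
- Pregnancy is not a graded toxicity, and cardiac failure was far more common on PIO (8.1% in Table 2) than bladder cancer (0.44% in 1.5.3). Naming the commoner risk and leaving rarer ones to grade-based rules is defensible. This is a fair argument for low priority.

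A reader might infer that PIO cannot be stopped for these events, or that the rules always let it continue. The documents support neither: stopping is possible at any time, and continuation without a hold depends on a grade the documents do not assign.

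**Conclusion.** The gap is real but narrow. Two conditions that bar a patient from starting PIO have no matching on-study dosing rule, and no provision requires PIO to be withheld until visible hematuria has been investigated. Followed literally, the rules permit continuation and escalation if the event is graded 1, and resumption without investigation after grade 2 or a first grade 3 episode.

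The size is small: about 0.02 to 0.07 expected bladder cancers in 26 subjects over one year. This assumes that rates from the pioglitazone studies summarised in 1.5.3 carry over to these subjects. It would be wrong to read 6.9% as the likely risk; the cohort rates give 1.8% to 2.6%. These figures describe bladder cancer, not hematuria. It would also be wrong to infer any effect on the efficacy conclusion or the two-stage design. This is a minor, inexpensive safety improvement.

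**What to change.** - Add a footnote to Table 4: *Gross (visible) hematuria of any grade: hold PIO at once, in addition to the immediate action in the row for its grade; do not resume PIO until the hematuria has been investigated and bladder cancer excluded, then follow the later action for its grade.* This order keeps the immediate hold of PIO and TKI at grade 3 or higher.
- State in 3.1, 5.2.4 and 7.1 that the increase to 45 mg does not occur while gross hematuria is uninvestigated.
- Add to 5.5: *New diagnosis of bladder cancer.*

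The cost is amendment wording, with no new scheduled visits or tests. The downside is an occasional PIO interruption, and unscheduled clinical work-up, for hematuria that proves benign. Under 5.5 an interruption of more than 28 days for a related event ends PIO, so the amendment should say whether time spent waiting for the work-up counts towards that limit.

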1.6 Rationale for the Study

New approaches are needed for the management of the 50% of CML patients who experience a molecular relapse following a first trial of TKI discontinuation. Given the potential risks of long-term TKI exposure, the contra-indication for pregnancies/child conception while on TKI, and the expenses associated with the use of these agents (92,000 USD/year for IM, > 120,000 USD/year for DAS or NIL), many patients express interests in TKI discontinuation trials. However, with the low success rate of a second discontinuation trial (20%), patients who fail their first TKI discontinuation have currently no other option but to continue TKI therapy.

Given the interactions between PPAR γ and STAT5 in CML LSCs, the synergy between PIO and IM [41], and the safety profile of PIO, a trial testing the combination of PIO and TKIs is a reasonable novel approach to eradicate minimal residual disease in CML .

2. Study Objectives and Hypothesis

2.1 *Objectives*

- To assess safety of the combination of PIO and TKI in CML subjects who experience a loss of MMR following a first TKI discontinuation
- To assess survival without loss of MMR following a second TKI discontinuation in subjects who achieve or maintain \leq MR^{4,5} with the combination PIO and TKI administered for at least 6 months

2.2 *Hypothesis*

Subjects who lose MMR after a first TKI discontinuation trial, but are still in CCyR and CHR regardless of their molecular status, will be offered enrollment on this trial. We hypothesize that PIO in combination with TKI will be well tolerated and that subjects will achieve or maintain \leq MR^{4,5} with the combination of TKI and PIO. Subjects who achieve \leq MR^{4,5} will be offered a second TKI discontinuation trial. We also hypothesize that MMR will be sustained following a second TKI discontinuation in at least 50% of subjects.

3. Investigational Plan

3.1 *Overall Study Design and Plan*

This is an open-label phase 2 study in which eligible subjects will receive PIO in combination with TKI. Safety of PIO in combination with TKI will be assessed continuously. Subjects who lose MMR while on the combination will be taken off study and managed at the discretion of the treating physician. Loss of MMR is defined by a detectable *BCR-ABL1* level $>0.1\%$ and confirmed within 4 weeks. For the purposes of this protocol and all analyses, a cycle of treatment is defined as 28 days. Study schema is depicted in Figure 7.

[figure not shown]

Figure 7. Study schema

Subjects may enter the study before or after restarting the TKI that was previously discontinued. Disease status can therefore be $>$ MMR but still in CCyR and CHR or \leq MMR. Subject will start PIO in addition to TKI, at 30mg/d for 2 cycles (56 days) and, in the absence of grade 2 or higher toxicities, PIO doses will be increased to 45mg/d. If grade 2 or higher toxicities occur on PIO 45 mg/d, PIO dose will be held until toxicities are \leq grade 1, and PIO doses will be decreased to 30 mg/d (**Dose modification was described section 7.1**). Subjects will receive PIO in addition to TKI for 6 months from the first documented \leq MR^{4,5}. During the combination of PIO and TKI, subjects will be monitored by blood qRT-PCR for *BCR-ABL1* obtained monthly.

Subjects entering the study in $>$ MMR but still in CCyR and CHR who do not achieve MMR within 4 months of the combination of PIO and TKI will be taken off study. Subjects entering the study in \leq MMR or who achieve MMR within 4 months of combination of PIO and TKI, will receive PIO for 6 months from the first documented \leq MR^{4,5}. Subjects who lose MMR at any time on the combination of PIO and TKI will be taken off treatment. Subjects who fail to achieve \leq MR^{4,5} after 6 months of the combination will also be taken off treatment. Fluctuations of PCR from MR^{4,5} at \leq MMR levels are expected and are acceptable during the combination of PIO and TKI.

Subjects who maintain \leq MR^{4,5} for 6 months with less or equal than 2 *BCR/ABL1* transcript fluctuation $<$ MMR will be eligible for a second TKI discontinuation trial. Subjects who discontinue TKI will be monitored by blood qRT-PCR for *BCR-ABL1* obtained monthly for the first 3 months, quarterly for 1 year, and then bi-annually for 1 year. After 2 years of follow-up off TKI, or if MMR is lost off TKI, subjects will have completed their participation on the trial and will enter the Long-Term Follow-up which includes once a year update on disease status (qRT-PCRs) for 5 years.

